# 3.2 Study Duration

We anticipate completion of enrollment with approximately 1.5 years. Each subject will participate in the study for 3 months (one 3 week post-procedure visit and one 3 month post-procedure visit). Charts will be reviewed for approximately 6-12 months after procedure completion.

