# 4.2 Dosage, Preparation and Administration

The physician will inject 10 mL of (100u/10mL) Botulinum Toxin A in either one or ten sites located in the midline, supra-trigonal posterior bladder wall at a depth of 3mm into the detrusor. Each participant will undergo one injection procedure for the duration of the study.

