### 9.2 Secondary Endpoints

The secondary outcome variables will include UTI rate, PVR, urinary retention, interinjection interval, catheter use within 3 months, PGI-I, and VAS pain score.

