### 12.3 Final Analysis Plan

We will describe the study population, including patient age, race/ethnicity, baseline severity scores (OAB-Q), BMI, medical history (prior surgery, menopausal status, prior Botox, etc.), overall, by arm, and stratified by study site (KPSC, UCI, PSJH). We will summarize continuous measures using means and standard deviations and categorical measures using percentages. We will compare study arms using the t-test or Fisher's exact test, as appropriate.

We will examine the outcome measures (OAB-Q and any secondary measures) to determine whether they are approximately normally distributed. If not, we will apply a

transformation prior to analysis to make the analytic variable approximately normal. If no transformation successfully achieves approximate normality, we will apply non-parametric tests for analysis, including Wilcoxon's rank-sum test instead of the t-test and quantile regression instead of linear regression.

We will analyze the main study outcome (OAB-Q score) initially using a t-test to compare the two study arms, overall and stratified by study site. We will further analyze the outcome using generalized estimating equations to account for correlation within study sites. These models will adjust for any potential differences in age, race/ethnicity, baseline severity scores, or any other baseline measures, and will account for any potential differences between study sites.

Secondary outcomes will be analyzed in the same manner as the primary outcome.

Primary analyses will be performed using intention-to-treat to determine study arm. If multiple individuals are not treated according to the randomization plan, we will perform a sensitivity analysis using as-treated, per-protocol study arms.

For any individuals who are lost to follow-up, we will first compare those individuals who are lost to those who complete follow-up in terms of demographics, baseline characteristics and any outcome assessments prior to the time that they are lost to follow-up. For primary analysis of OAB-Q scores, we will analyze complete data including only those who have completed the follow-up questionnaires within the prescribed timeframes. If more than 10% are lost to follow-up, we will additionally perform multiple imputation in an attempt to capture data of those lost to follow-up.

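### Inter-injection interval is right-censored by the chart review, but section 12.3 gives it the primary outcome's t-test or rank-test path with no censoring method and no rule for women not re-injected

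*Combined protocol and SAP*

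**What the plan says.** Section 9.2 lists seven secondary outcomes: "UTI rate, PVR, urinary retention, interinjection interval, catheter use within 3 months, PGI-I, and VAS pain score". No section defines the start, end event or unit of the inter-injection interval.

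Three statements fix what can be observed:
- Section 4.2: "Each participant will undergo one injection procedure for the duration of the study".
- Section 3.2, active participation: "Each subject will participate in the study for 3 months".
- Section 3.2, after that: "Charts will be reviewed for approximately 6-12 months after procedure completion".

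Section 12.3 then covers all seven outcomes in one sentence: "Secondary outcomes will be analyzed in the same manner as the primary outcome". For the primary outcome that means comparing arms "initially using a t-test to compare the two study arms, overall and stratified by study site", followed by GEE models with covariates. If normality fails even after transformation, the fallback is non-parametric, "including Wilcoxon's rank-sum test instead of the t-test and quantile regression instead of linear regression".

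The missing-data text in 12.3 has two parts. The first, for the primary OAB-Q analysis, is "we will analyze complete data including only those who have completed the follow-up questionnaires within the prescribed timeframes". The second adds multiple imputation if loss to follow-up exceeds 10%.

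**The concern.** With one study injection and a chart review after it, the interval that fits the design runs from the study injection to the next. A woman not re-injected by the end of her review has an interval known only to exceed her review time. The methods that 12.3 names need one number per woman, and the plan supplies none for her. An analyst must drop her, enter her review time, or rank her last, and the plan does not choose.

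At stake is the only listed outcome that measures how long the effect lasts beyond the 3-month visit; OAB-Q and PGI-I collection stops there. Section 1.1 cites similar durability in an earlier pilot study as part of the case for a single site. Two analysts who both follow 12.3 could report different durability results from the same data.

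**Working it through.** **Plan's own figure.** None exists for this outcome. The sample size belongs to the primary outcome and is used here only for the number per arm. With SD 20, margin 10, 80% power and one-sided 5%, n = 2 × (20/10)² × (1.645 + 0.842)² = 49.5, so 50 per arm; the noncentral-t version gives the plan's 51.

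**Assumed inputs, none from the documents.** Interval T is Weibull with survival S(t) = exp(−ln 2 × (t/m)^k), median m = 7 v 9 months, shape k = 1.5, 2 or 3. Review end C is uniform over 6-12 months in both arms, so G(t) = P(C > t) is 1 up to 6 months and (12 − t)/6 after that. The 6-12 range is from section 3.2; its uniform spread is assumed.

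**Three quantities per arm** (f is the density of T):
1. Restricted mean to 12 months: R(12) = ∫₀¹² S(t) dt.
2. Re-injected women only: E[T | T ≤ C] = ∫ t f(t) G(t) dt ÷ ∫ f(t) G(t) dt.
3. Review time as the interval: E[min(T, C)] = ∫ S(t) G(t) dt = (1/6) ∫₆¹² R(u) du.

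The last equality matters: with the same review pattern in both arms, review-time coding estimates the restricted mean averaged over horizons from 6 to 12 months.

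**Numbers put in, shape 2 (9-month arm minus 7-month arm).**
- R(12): 8.465 − 7.127 = 1.338 months.
- Re-injected only: 5.773 − 5.394 = 0.379.
- Review time: 7.176 − 6.362 = 0.814.

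**All shapes, by integration.**

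| | k = 1.5 | k = 2 | k = 3 |
|---|---|---|---|
| Re-injected within review, 7 v 9 months | 63% v 49% | 67% v 50% | 73% v 50% |
| 12-month restricted difference (months) | 1.10 | 1.34 | 1.68 |
| Re-injected only | 0.27 | 0.38 | 0.64 |
| Review time as interval | 0.69 | 0.81 | 0.99 |

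Simulation with 1,000,000 intervals per arm agrees to within 0.01 month. Kaplan-Meier restricted means to 12 months, over 8,000 simulated trials of 51 per arm with the same censoring, recover 1.10/1.34/1.67.

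**Power at 51 per arm (6,000 simulated trials).**

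| | k = 1.5 | k = 2 | k = 3 |
|---|---|---|---|
| t-test, re-injected only | 7% | 9% | 21% |
| t-test, review time | 23% | 36% | 67% |
| Log-rank | 30% | 49% | 84% |

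**No true difference** (8 v 8 months, same review pattern): rejection rates are 4.6-5.3% for all three.

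**Unequal review length.** Take no true difference, median 8 and shape 2 in both arms, with one arm reviewed to 6 months and the other to 12, the extremes of the stated range. Review-time coding then gives R(12) − R(6) = 7.857 − 5.304 = 2.55 months from review length alone. This is a bound, not a forecast.

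**Different distribution.** Lognormal intervals (log-SD 0.5, control median 9 months, study/control ratio 0.75, same review pattern) leave 52% of control and 31% of study intervals censored. The unrestricted mean difference of −2.55 months becomes −0.81 (re-injected only) or −1.06 (review time). Power is 33%, 69% and, for log-rank, 73%.

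**The case against.** The strongest case for the plan has four parts.

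First, review-time coding is not biased when both arms are reviewed alike. That stands. A reader might score its 0.69/0.81/0.99 against the 12-month 1.10/1.34/1.68 and call the gap a loss, but the documents set no 12-month target; the gap is a difference in horizon. The same holds for an apparent sign reversal. With median 7, shape 3 against median 7.5, shape 1.2, the 12-month difference is +0.31 and the review-time value −0.34, yet the restricted difference is itself −0.43 at 9 months and −0.65 at 6. The curves cross, and review time reports that correctly for its horizon. Only the re-injected-only value of −1.72 is a coding distortion.

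Second, a reader might infer that the plan drops women not re-injected. It does not say so. The complete-data rule is written for OAB-Q questionnaires, and this outcome comes from charts. Dropping them is one open choice, not a stated one.

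Third, the non-parametric fallback is open-ended and could admit a log-rank test. But non-normality triggers it, not censoring, and it gives no event, censoring date or coding rule. Imputation does not fill the gap either: a woman whose chart was fully reviewed without re-injection is not lost to follow-up.

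Fourth, the stated range may be a planning range with one review length for all, and the case report form (Appendix A, not visible here) may define the dates. One common length would make a Wilcoxon test with women not re-injected ranked last workable. The analysis plan would still need to say so.

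**Conclusion.** The point holds as a mismatch between a right-censored outcome and the methods assigned to it, with an open analyst choice as the result. It deserves correction before the analysis but does not threaten the trial's main conclusion.

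If only re-injected women are analysed, the difference is distorted: about 24%, 28% and 38% of the 12-month restricted difference remains (0.27/1.10, 0.38/1.34, 0.64/1.68). If review time is used, the contrast is valid under equal review but refers to an unstated 6-12 month horizon, has somewhat less power than log-rank, and becomes biased if review length differs by arm.

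All sizes rest on assumed distributions; the text alone supports the gap, not its magnitude. A reader might infer inflated false positives, but error stays near 5% with no true difference and equal review. Nor do the documents support any effect on the primary OAB-Q analysis or the sample size. This is one of seven secondary outcomes, and no stated hypothesis rests on it.

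**What to change.** In section 12.3:
- Exempt inter-injection interval from the sentence that extends the primary methods to all secondary outcomes.
- Define it as time from the study injection to the next intradetrusor injection.
- Report Kaplan-Meier curves by arm, with a log-rank test or Cox model stratified by site.
- Censor women not re-injected at the earlier of the last documented contact in the health system and one common chart-review cut-off applied to both arms. Using the date the chart was opened would count a woman who has left the system as event-free.
- State the horizon of any mean difference, for example a restricted mean to that cut-off.

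If a rank test is preferred, every chart must reach the cut-off, and the plan must say that women not re-injected rank last. The cut-off then drives power: under the Weibull assumptions above, 21/30/49% at 6 months and 34/55/89% at 12 months.

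The cost is SAP wording and at most one recorded date per woman, if the case report form does not already hold it. There are no new visits or patients, and this point asks for no change to the other secondary outcomes.

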# 1.2 Hypothesis

We hypothesize that one injection of intradetrusor Botox® will have similar efficacy to ten injections, better tolerability, due to decreased procedure time and less pain, along with potential for lower adverse event rates, specifically urinary retention and urinary tract infections.

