### 12.2 Sample Size Considerations

The target sample size was determined by using the typical standard deviation of the OAB-q symptom severity score (20 points per literature review) and the known minimally important clinical difference of 10 points of the OAB-q severity subscale, our primary outcome. Using this data, we calculated the sample size of N=102 maximum total (expect to enroll ~40 at KP, ~60 at UCI, ~20 PSJH), 51 subjects in each arm for an 80% power with 5% significance level. Based on review of prior clinical data at UCI and KP, we expect to complete enrollment within 1 – 1.5 years. With an estimated 15% lost to follow up rate, we calculated need to enroll 116 subjects.

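### Section 12.3 puts the yes/no secondary outcomes on a continuous-outcome path whose fallback regression is uninformative at low event rates, and names no effect measure for them

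*Combined protocol and SAP*

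**What the plan says.** Section 9.2 lists the secondary endpoints: "The secondary outcome variables will include UTI rate, PVR, urinary retention, interinjection interval, catheter use within 3 months, PGI-I, and VAS pain score". They are of mixed type. Retention and catheter use are naturally yes/no, and UTI is too if it is counted per woman. PGI-I is a rating. PVR, VAS pain and the inter-injection interval are continuous.

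Section 12.3 treats them all alike:

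- The distribution check covers everything: "We will examine the outcome measures (OAB-Q and any secondary measures) to determine whether they are approximately normally distributed". A transformation is tried next. If none works, the plan turns to non-parametric methods, among them "Wilcoxon's rank-sum test instead of the t-test and quantile regression instead of linear regression".
- The primary outcome is compared by t-test, and then: "We will further analyze the outcome using generalized estimating equations to account for correlation within study sites". Those models adjust for baseline measures and site.
- The secondary outcomes get one sentence: "Secondary outcomes will be analyzed in the same manner as the primary outcome".

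A categorical test does appear in Section 12.3, in the paragraph that describes the study population: "We will compare study arms using the t-test or Fisher's exact test, as appropriate". The paragraphs on outcomes do not repeat it.

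Section 1.2 gives the safety outcomes a role in the hypothesis. It expects one injection to be better tolerated, "along with potential for lower adverse event rates, specifically urinary retention and urinary tract infections".

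**The concern.** The path in Section 12.3 is built for a score such as the OAB-q. A yes/no outcome fails the normality check every time, and no transformation rescues it. What remains is a rank test, which yields a p-value but no effect size, and a quantile regression, which suits 0/1 data poorly. The plan names no binary-outcome model, no link, no risk difference or odds ratio, and no confidence interval for retention, UTI or catheter use.

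At stake is the comparison behind the safety part of the hypothesis. An analyst following the text literally could report an adjusted arm effect of 0 for an outcome on which the arms differ widely. An analyst who departs from the text would choose the test and effect measure after seeing the data.

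**Working it through.** **Inputs.** The arm size of 51 is from Section 12.2. The documents give no event rates, so every event count and rate below is an assumption for illustration. Differences are one injection minus ten.

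**The plan's own figure.** Section 12.2 sizes the primary outcome only, from the "typical standard deviation of the OAB-q symptom severity score (20 points per literature review") and a difference of 10, so the standardised difference is 10/20 = 0.5. A t-based calculation at one-sided 5% and 80% power gives 50.15, rounded up to 51 per arm, or 102 in total. The sidedness is not stated; two-sided 5% would need 64 per arm. No figure is given for any yes/no outcome, so 51 serves here only as the arm size.

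**Step 1: transformation.** For y equal to 0 or 1, any transformation g satisfies g(y) = g(0) + [g(1) - g(0)] × y. The result still takes two values and is a linear relabelling of y. It cannot become normal, and the t-test p-value does not change. The rule therefore always ends at the fallback.

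**Step 2: median regression without covariates.** The fitted arm effect is the difference between the two sample medians. With 51 women the median is the 26th ordered value.

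- 3/51 events: 48 zeros, so the 26th value is 0.
- 20/51 events: 31 zeros, so the 26th value is 0.
- Arm effect: 0 - 0 = 0.

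This holds whenever each arm has 25 or fewer events. Another quantile does not help: a sample quantile of 0/1 data is itself 0 or 1, so the difference can only be 0, +1 or -1. At the 75th percentile, the 39th ordered value is 0 in the first arm and 1 in the second, giving -1. None of these is a risk difference.

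**Step 3: what a risk difference shows for the same counts.** 3/51 = 5.88% (Wilson 95% limits 2.02% to 15.92%); 20/51 = 39.22% (27.03% to 52.91%). Difference: 5.88 - 39.22 = -33.3 points. Newcombe limits:

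- lower: -33.33 - √[(5.88 - 2.02)² + (52.91 - 39.22)²] = -33.33 - 14.23 = -47.6
- upper: -33.33 + √[(15.92 - 5.88)² + (39.22 - 27.03)²] = -33.33 + 15.79 = -17.5

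That is -33 points (95% CI -48 to -18), against a median effect of 0.

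**Step 4: median regression with covariates.** Simulation, 300 trials per pair of assumed rates, 51 per arm, adjusted for age, baseline score and site:

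| Assumed rates, one vs ten injections | Trials with an adjusted arm effect of exactly 0 |
|---|---|
| 2% vs 6% | 100% |
| 5% vs 15% | 100% |
| 10% vs 20% | 100% |
| 15% vs 30% | 100% |
| 20% vs 40% | 93% |
| 30% vs 45% | 73% |
| 40% vs 60% | 17% |

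The adjusted effect is 0 at low rates and increasingly often non-zero as a rate approaches or passes one half.

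**Step 5: the unadjusted tests.** For 2/51 versus 8/51, p is 0.046 (t-test), 0.048 (Wilcoxon) and 0.092 (Fisher). In the Step 4 simulations the Wilcoxon test rejected as often as the uncorrected chi-square test in every scenario, for example 39% at 5% versus 15%. It detects a difference. However, whether Fisher's test applies to outcomes can decide which side of 5% a result falls on.

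**The case against.** The strongest reply is that much of the plan still works. The adjusted model that Section 12.3 names is a GEE, and analysing the secondaries like the primary carries it over. With an identity link and arm as the only term, a GEE on 3/51 versus 20/51 returns -0.333, the very difference that the median regression misses. A logit link is equally compatible with the text. The Wilcoxon test on 0/1 data is close to a chi-square test. Fisher's exact test is named in the section, crude percentages are always available, and the list of non-parametric methods is worded as open-ended.

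All of that stands, and it rules out two stronger readings. A reader might infer that the adjusted effect is zero by construction; that needs the median, which is not named, and event proportions below one half in both arms, and with covariates it is a tendency at low rates rather than an identity. A reader might also infer that the safety benefit cannot be estimated; the crude difference and a suitably specified GEE can both estimate it.

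The reply does not remove the gap. The GEE has no stated family or link, and the text does not say whether quantile regression replaces it once normality fails. Fisher's test is attached to the description of the population. Each rescue requires a choice that the plan has not made.

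**Conclusion.** The point holds as a misdirected and underspecified analysis of the yes/no secondary outcomes. Read literally, Section 12.3 sends them to a fallback that, at the median and with events in fewer than half the women in each arm, gives an unadjusted arm effect of 0 whatever the data, and an adjusted effect that is nearly always 0 at low rates. In the assumed example this hides a difference of 33 points. The Wilcoxon test remains usable but supplies no effect size.

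The conclusion rests on three assumptions: the median is the intended quantile, UTI is counted per woman (Section 9.2 speaks only of a rate), and event proportions are below one half. A reader might go further and assume that very few events will occur, so that any adjusted model must fail; the documents give no event rates and do not support that.

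The primary analysis is untouched. This should be fixed, but its reach is limited to secondary outcomes.

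**What to change.** In Section 12.3:

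- Limit the normality check, transformation and quantile-regression path to continuous measures, and keep the existing sentence on secondary outcomes for the continuous ones only (PVR, VAS pain, inter-injection interval).
- For UTI, retention and catheter use, report number and percent per arm, the risk difference with 95% CI, and Fisher's exact test, at most stratified by site. State whether UTI is counted per woman.
- Say that the interval is the main result. Test and interval can disagree near 5%: for assumed counts of 5/51 versus 13/51, Fisher's p is 0.067 while an identity-link interval is -0.302 to -0.012.
- Analyse PGI-I with a rank or ordinal method.
- If a GEE is kept for any yes/no outcome, state its family and link, and that quantile regression does not replace it.

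The cost is SAP wording only, with no new data, visits or participants. It should be settled before outcome data are compared by arm, so that the test and effect measure are not chosen after the fact.

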**Pre-Procedure Requirements** 

Prior to the procedure each subject will have the following (at either prior/consultation visit or procedure visit see study calendar below):

[] sign consent form
(prior to any non-standard of care procedures)
[] Post-void residual
[] Urinalysis (formal UA OR poct udip)
[] OAB-Q LF Questionnaire completion

[figure not shown]

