1. Procedure visit for intradetrusor Botox® injection, collection of pre-procedure OAB-q, VAS pain scale after procedure

2. 3-week follow up visit, including collection of post-void residual via urethral catheterization or bladder scan (ultrasound) and post-procedure OAB-q

3. 3-month follow up visit, either in person or via telephone with collection of OAB-g and symptoms improvement questionnaire (PGI-I)

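### Section 12.3 leaves adjustment of the PVR comparison for pre-injection PVR open; it should be a fixed covariate in a named main PVR analysis.

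*Combined protocol and SAP*

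**What the plan says.** Section 9.2 lists PVR and urinary retention as two separate secondary outcomes. The Pre-Procedure Requirements under section 8.1.2 include "Post-void residual" for every subject. Section 8.2.1 and the schedule in section 8.4 collect it again at the 3-week visit. Each woman followed to 3 weeks should therefore have a pair of values.

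Section 12.3 has no paragraph for PVR. It states: "Secondary outcomes will be analyzed in the same manner as the primary outcome". The primary outcome is analysed in two steps:

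- **First step:** "initially using a t-test to compare the two study arms, overall and stratified by study site". If no transformation gives approximate normality, Wilcoxon's rank-sum test replaces the t-test and quantile regression replaces linear regression.
- **Second step:** "We will further analyze the outcome using generalized estimating equations to account for correlation within study sites". On covariates: "These models will adjust for any potential differences in age, race/ethnicity, baseline severity scores, or any other baseline measures". The same section, in its list of baseline characteristics, identifies the severity scores as OAB-Q.

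Baseline PVR is not named in the covariate sentence or in the list of baseline characteristics to be described. Section 12.1 frames the OAB-Q hypothesis as change from pre-procedure to 3 weeks. Nothing says whether PVR is handled the same way.

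**The concern.** A woman's PVR before injection is the natural predictor of her PVR three weeks later. If it is left out of the comparison, between-woman variation that was present before treatment stays in the error term, and a chance imbalance in baseline PVR goes straight into the estimated arm difference.

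The plan, carried over to PVR as written, leaves three things open:

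1. The first step has no baseline covariate.
2. The only baseline outcome value named for the second step is a symptom score, not the volume being analysed. Baseline PVR depends on the open clause, which is worded around potential differences. That can be read as adjusting only where the arms look different. The precision gained from a prognostic covariate does not depend on imbalance, and a covariate set fixed only after the data are seen is open to choice.
3. The form of the outcome (3-week value or change) and the deciding step are not stated.

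At stake is the precision of one continuous secondary safety measure and the reproducibility of its analysis.

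**Working it through.** **The plan's own figure.** Section 12.2 gives 51 per arm, 80% power and 5% significance for OAB-q severity, with SD 20 and difference 10. Normal formula: n per arm = 2(z_alpha + z_beta)² × SD²/difference².

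- One-sided 5%: 2 × (1.645 + 0.842)² × 400/100 = 49.5, so 50. The t-based version needs 50.15, so 51, or 102 in total. This reproduces the plan.
- Two-sided 5%: 2 × (1.960 + 0.842)² × 4 = 62.8, so 63 per arm, or 126. This does not.

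The figure concerns the primary outcome only. The documents give no sample size, power, SD, target difference or pre/post correlation for PVR.

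**Inputs for PVR.**
- n = 51 per arm (section 12.2).
- Two-sided 5%: assumed.
- rho, the correlation of baseline with 3-week PVR: assumed, shown over 0.1 to 0.6.
- d, the arm difference in units of the SD of 3-week PVR: set so that a plain t-test on 3-week PVR has 80% power. By the noncentral t with 100 degrees of freedom, d = 0.560.
- Equal SDs before and after: assumed, for the change-score column.

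**Formulas.**
- Adjusted for baseline: residual SD = SD × sqrt(1 − rho²), so the effective difference is d/sqrt(1 − rho²).
- Unadjusted change score: SD of change = SD × sqrt(2(1 − rho)), so the effective difference is d/sqrt(2(1 − rho)).

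Example at rho 0.5: 0.560/sqrt(0.75) = 0.647, power 89.9%. Example for change at rho 0.3: 0.560/sqrt(1.4) = 0.473, power 65.8%.

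| rho | variance removed (rho²) | t-test, 3-week value | adjusted for baseline | unadjusted change |
|---|---|---|---|---|
| 0.1 | 1% | 80% | 80.4% | 55.1% |
| 0.2 | 4% | 80% | 81.6% | 60.1% |
| 0.3 | 9% | 80% | 83.6% | 65.8% |
| 0.4 | 16% | 80% | 86.4% | 72.5% |
| 0.5 | 25% | 80% | 89.9% | 80.0% |
| 0.6 | 36% | 80% | 93.8% | 87.9% |

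From a 60% starting point (d = 0.443), adjustment gives 64.1% at rho 0.3 and 72.4% at rho 0.5. With an assumed difference of 0.5 SD and the normal approximation, 71.4% becomes 71.8% at rho 0.1, 75.4% at 0.3 and 83.0% at 0.5. The pattern is the same: almost nothing at 0.1 to 0.2, and a material gain from about 0.4 upward.

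The adjusted analysis is at least as precise as either alternative at every rho shown, apart from one degree of freedom. The change score matches the 3-week t-test only at rho 0.5 and is worse below that.

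**The case against.** The strongest reply is that the plan already allows this adjustment. The GEE models are to "adjust for any potential differences in age, race/ethnicity, baseline severity scores, or any other baseline measures". PVR taken before injection is a baseline measure, so it falls within that clause, and the clause is aimed at chance imbalance. Nor does the plan say that the t-test decides. This stands as far as it goes: a reader might infer that the later model leaves baseline PVR out, or has OAB-Q as its only covariate, and the text supports neither. Age and race/ethnicity are also named, and the clause is open. What remains is that the adjustment is discretionary and the deciding analysis unnamed.

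Second, if PVR follows section 12.1 and is tested as change, the first step does use the baseline value. That is possible and the documents do not settle it. It does not rescue the plan: at rho below 0.5 an unadjusted change score is less precise than the plain 3-week comparison.

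Third, a reader might infer that the retention comparison itself is weakened. The documents do not support that. Section 9.2 lists urinary retention separately, and adjusting continuous PVR leaves the comparison of retention rates unchanged, even though section 8.2.2 uses the 3-week PVR to evaluate retention.

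Fourth, a material loss of power cannot be shown from the documents. Several features could lower rho: exclusion of retention at entry (PVR above 150 cc on two occasions) narrows the baseline range; the baseline value may come from the earlier consultation visit, possibly before the wash-out; and the 3-week value may be taken by catheter or ultrasound. PVR may also be skewed enough for the rank-based route, where these normal-theory figures are only a guide. All of this stands and limits the point to an improvement.

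**Conclusion.** The point holds as a minor improvement. Section 12.3 does not fix baseline PVR as a covariate for the PVR comparison, does not say whether the 3-week value or the change is tested, and does not name the deciding step. The comparison may therefore be less precise than data already collected would allow, and its covariate set can be chosen late.

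The direction is certain for a t-test on 3-week PVR whenever rho is appreciably above zero. The size is conditional: with 51 per arm and two-sided 5%, 80% power becomes about 80%, 82%, 84%, 86% and 90% at rho 0.1, 0.2, 0.3, 0.4 and 0.5. If an unadjusted change score were used, power for the same difference would be about 66% at rho 0.3. These figures rest on an assumed rho, an assumed detectable difference, approximate normality and, for change, equal SDs. PVR is not the outcome on which the trial was sized.

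**What to change.** In section 12.3, give PVR its own sentences, for example:

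*The main analysis of PVR will compare 3-week PVR between arms in a regression model with baseline PVR as a fixed, prespecified covariate, included whether or not the arms differ at baseline, and with study site accounted for as planned for the primary outcome. The same transformation, one that allows 0 mL, will be applied to both values. If no transformation is adequate, baseline PVR will be included as a covariate in the planned quantile regression.*

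Add baseline PVR to the list of baseline characteristics, overall, by arm and by site. The t-test or Wilcoxon comparison can stay as a supporting result.

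The cost is a short change of wording and one degree of freedom. No new measurement, visit or patient is needed. If rho turns out low, little is gained and almost nothing is lost.
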